A Randomized Control Trial Investigating the impact of High dose Prophylactic Tranexamic acid on blood loss at the time of minimally invasive myomectomy – Protocol

Proposed Research Study:

A Randomized Control Trial Investigating the impact of High dose Prophylactic Tranexamic acid on blood loss at the time of minimally invasive myomectomy

Investigators:

[name] [name] MD [name] [name] MD [name], PhD [name] [name] MD

Specific aim:

- 1. To compare the volume of blood loss in patients undergoing minimal invasive myomectomies who received prophylactic tranexamic acid vs placebo
- 2. To compare the number of blood products received during/post procedure in patients received tranexamic acid prophylactically vs placebo

This will be conducted as a double blinded randomized control trial. Data will be collected over a 3 year period with the goal of recruiting 50 patients per arm

Background and Significance

In minimal invasive gynecologic surgeries, operative blood loss is a common complication that affects postoperative morbidity and recovery (1). Antifibrinolytic drugs are well established in the management of surgical and traumatic bleeding(1–3). Tranexamic acid (TXA) is a synthetic lysine derivative that binds to plasminogen and inhibits the enzyme from breaking down fibrin deposits. In a recent Cochrane review last updated in 2015 that investigated the use of TXA in general surgery, TXA was found to reduce intraoperative and postoperative blood loss by 414 mL (95% confidence interval [CI] –525 to –303 mL) in comparison to placebo(4). In another Cochrane review 16 trials involving benign obstetrics and gynecologic were included. 14 studies involved women undergoing elective Cesarean deliveries and 2 studies involved women having abdominal myomectomy. No studies involving hysterectomy were identified and no studies involving minimal invasive myomectomies were identified(1)(5). Only recently, the first Randomized controlled double blind study was completed at George Washington University (6).

The results of this study have yet to be published. We hope to attempt to show the efficacy of prophylactic TXA use in minimal invasive myomectomies in reducing blood loss.

Study Design

This is a Double-blinded randomized placebo-controlled trial based at Eastern Virginia Medical School. Subjects who are identified in clinic having menorrhagia or abnormal Uterine bleeding (AUB) due to uterine fibroids and meet inclusion criteria based on the ultrasound (US) or Magnetic Resonance Imaging (MRI), aged 18-45 undergoing laparoscopic or Robotic assisted myomectomies. These subjects will be then approached for consent during their pre-op visit 1-2 weeks prior to their surgery. The setting for consent will be in a patient consultation room. A total of 50 women in each arm of the study with symptomatic fibroids meeting any of the following criteria will be included in the study:

1) At least one fibroid greater than or equal to 6 cm (7)

2) Any intramural or broad ligament fibroid greater than or equal to 4 cm (7)

3) At least 3 total fibroids based on preoperative imaging. (8)

Randomization will be performed using an automated randomization website (9)(Supplement 1)

Patients will be randomized to receive a single IV bolus injection of TXA 30mg/kg in 50ml of normal saline (intervention group) versus an IV bolus injection of normal saline of equivalent volume (placebo group) 15 minutes prior to initial surgical incision. This dosage will not be adjusted for patients with renal insufficiency as they will be excluded from the study. Preparation of the medications will be performed by anesthesia who have both medication and normal saline available to them on short notice. No prior preparation by pharmacy will be required. Tranexamic acid is readily available in a 10 ml vial, which does not need a pharmacist to prepare for administration. The vial is mixed with 50 ml of saline in the operating room. This is the same process that occurs outside of any study with any medication that is administered intra-operatively. This will in no way impact the patient's safety during the surgery, especially since it is administered 15 minutes prior to the start of the procedure.

The dosage of TXA is considered a high dose and has been shown in cardiothoracic, orthopedic and trauma surgery to be reduce blood loss and transfusion need in comparison to regular dosing. There has been no reported increases in TXA side effects with higher dosing of TXA in the literature. (10–12)

Both surgeon and patient will be blinded to the treatment arm. This dosage has been used previously in both obstetric and gynecological procedures and is the same dose recommended by the WHO for preventing post-partum hemorrhage(13).

The surgery itself will be scheduled at either Sentara Norfolk General, Sentara Leigh hospital, and Sentara Princess Anne hospital. These are the three sites that the investigators already perform Minimally invasive myomectomies.

An envelope will be given to the anesthesiologist prior to the procedure informing whether they are to receives TXA or the placebo. Blood loss will be estimated by the surgeon performing the procedure. Hemoglobin and hematocrit will be obtained 24 hours post procedure. The patient will be assessed for reported side effects from the medication given will be assessed by a questionnaire that will be given at their post-op appointment at the 2 week and 6-week mark. During these two visits a physical exam is performed, checking incision sites, and patient symptoms, all of which are standard of care for any minimally invasive procedure. The patients will be seen at the EVMS outpatient clinic for Gynecology or

depending with the physician who performed the surgery. Data will be collected from both Allscripts and EPIC charts.

Primary Outcomes measured

- 1. Estimated blood loss at time of procedure completion; using volume of cannister and weight of lap sponges
- 2. Calculated Blood loss, using pre-operative hematocrit, postoperative hematocrit and estimated blood volume x Body Mass Index
- 3. Number of blood products received during admission that is directly due to blood loss at time of procedure

Secondary outcomes

- 1. Duration of surgery
- 2. Length of hospital stay
- 3. Number of fibroids removed
- 4. Fibroid types 0-8
- 5. Total Weight of fibroids removed
- 6. Pain index on post-operative day 1, and 2-week post-operative visit
- 7. Post-operative complications
 - a. Readmission
 - b. Postoperative fever
 - c. Postoperative infection
- 8. Reported mild side effects of medication (Supplement 2)
 - a. Diarrhea
 - b. Nausea
 - c. Headache
- 9. Reported Serious Side effects of medication (Supplement 2)
 - a. Shortness of breath
 - b. Deep vein thrombosis
 - c. Pulmonary Embolism

Patient data will be collected in a data collection tool with the subjects de-identified.

A subject identifying tool will also be sued to identify the subject with their EPIC and Allscripts MRN.

Both epic and Allscripts will be used to collect patient data

Inclusion Criteria

- 1. Female
- 2. Age 18-45

- 3. Undergoing laparoscopic myomectomy
- 4. At least one fibroid greater than or equal to 6 cm
- 5. Any intramural or broad ligament fibroid greater than or equal to 4 cm
- 6. At least 3 total fibroids based on preoperative imaging

Exclusion Criteria

- 1. Severe existing medical complications involving the heart, liver, or kidney
- 2. Moderate to severe renal impairment (serum creatinine > 1.4)
- 3. Blood clotting abnormalities
- 4. Age <18
- 5. Known Allergies to tranexamic acid
- 6. Known Contraindications to Minimally invasive myomectomies
- 7. If you are pregnant
- 8. History of a prior blood clot in the lung, arm, or leg, known as pulmonary embolism or deep vein thrombosis
- 9. Any active blood clots, clotting disease, pulmonary embolism, cerebral thrombosis, estrogen use, renal impairment, elevated creatinine level
- 10. History of a stroke or mini-strokes

11. History of prior seizures

- 12. Concurrent oral contraceptive use
- 13. Contraindications to receiving Tranexamic acid
 - i. In patients with acquired defective color vision, since this prohibits measuring one endpoint that should be followed as a measure of toxicity
 - ii. In patients with subarachnoid hemorrhage. Anecdotal experience indicates that cerebral edema and cerebral infarction may be caused by tranexamic acid in such patients.
 - iii. In patients with active intravascular clotting.
 - iv. In patients with hypersensitivity to tranexamic acid or any of the ingredients

Statistical Analysis

Descriptive statistics will be calculated. Continuous variables will be compared with t-test and categorical variables will be compared with Chi-square. P-values of less than 0.05 will be considered significant. A logistic regression will be performed to calculated the adjusted odds ratio.

Sample size calculation was set at 90 % power to detect a 150 ml difference in blood loss, with a significant level of 5 % and a one-sided alpha of 0.05 and beta (β)-set at 0.1.

The sample size was calculated using the formula below.

N=2 Σ^{2} (z α +Z1/2 β)²/r²

Substituting with figures:

 $N=2\times135\times135(1.96+1.282)^2/150^2=17$ patients in each group.(14) However, we wish to include 50 patients on each arm to try to increase the chances of identifying any side effects associated with the procedure

Risks of Study

There are few risks associated with this study beyond the standard risks of confidentiality breach of patient private information and the general risks of minimally invasive gynecologic surgery. Tranexamic acid is commonly used for surgical procedures and reduces blood loss significantly. It is used in multiple specialties, such as general surgery, trauma surgery, gynecologic surgery, and obstetric surgery to minimize and prevent blood loss in patients. Even though it is an off-label use it has been studied extensively and is considered a safe and standard method to prevent /minimize blood loss. It is readily available intraoperatively at all Sentara facilities for use in a situation of excessive intraoperative blood loss. It is subject to shortages and unavailability as with any other medication.

Available below is the associated side effects of prolonged usage of IV tranexamic acid

>10%:

- Central nervous system: Headache
- Gastrointestinal: Abdominal pain
- Neuromuscular & skeletal: Back pain
- musculoskeletal pain
- Respiratory: Nasal signs and symptoms

1% to 10%:

- Central nervous system: Fatigue
- Hematologic & oncologic: Anemia
- Neuromuscular & skeletal: Joint pain
- Muscle cramps
- Muscle spasm

This study will only administer a single dose use of tranexamic acid, and we believe that there will be minimal side-effects comparatively.

In the event there are any serious adverse events, the principal investigator will notify FDA MedWatch, using their standard operating procedure, and the EVMS IRB using the Serious Adverse Event form appended to the protocol

Another risk associated with the study is health information confidentiality breach. To minimize the risk, the patient data will be stored in a single desktop computer located in the EVMS outpatient facility, with a password protected account. Access will be given only to those listed as coinvestigators on the study. The risks of the surgery and the drug cannot be minimized further.

Budget

Cost of tranexamic acid will be covered as medications given during surgery; It is covered by insurance for gynecologic surgery because it is considered a primary method of hemostasis for surgery. This medication is used routinely in myomectomies, and there has been no issue covering the cost of the medication as part of the surgery outside of this study. Since anesthesia is administrating the medication and will be the only person not blinded to the study, they will also bill for the medication. This is usually how the medication is billed under normal circumstances.

Since there is no current funding for this study, the patient will be informed of the cost of the medication and they can refuse to participate if they do not want to pay for such medication.

The placebo will be normal saline that will be administered by anesthesia. It is not considered an additional cost to the surgery because of its normal use during any procedure

References

- 7. Parker WH. Uterine myomas: management. Fertil Steril [Internet]. 2007 Aug 1;88(2):255–71. Available from: https://doi.org/10.1016/j.fertnstert.2007.06.044
- 8. Lam S-J, Best S, Kumar S. The impact of fibroid characteristics on pregnancy outcome. Am J Obstet Gynecol. 2014 Oct;211(4):395.e1-5.

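### Is the first primary outcome, intraoperative blood loss, too loosely defined to analyse because no netting rule is stated?

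*Combined protocol and SAP*

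**What the plan says.** Intraoperative blood loss is described twice. The Study Design text gives the assessor: "Blood loss will be estimated by the surgeon performing the procedure". The list under Primary Outcomes measured, item 1, gives the inputs: "Estimated blood loss at time of procedure completion; using volume of cannister and weight of lap sponges".

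Four other statements bear on the point:

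- Blinding (Study Design): "Both surgeon and patient will be blinded to the treatment arm".
- Data source (Study Design): "Data will be collected from both Allscripts and EPIC charts". A separate data collection tool is mentioned, but its fields are not in the supplied text.
- Item 2 of the primary outcomes is a second measure of blood loss: "Calculated Blood loss, using pre-operative hematocrit, postoperative hematocrit and estimated blood volume x Body Mass Index".
- Statistical Analysis: "Sample size calculation was set at 90 % power to detect a 150 ml difference in blood loss". It does not say which measure of blood loss is meant. The calculation gives 17 per group, and the plan enrols 50 per arm in order to see more of any side effects.

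The supplied text gives no formula for turning canister volume and sponge weight into millilitres of blood. It does not mention surgical irrigation. The only saline it describes is the intravenous placebo and the diluent for the study drug.

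**The concern.** A primary outcome should give one reproducible number per patient. Here the surgeon's estimate could be read as a visual judgement, as a gross total of canister and sponges, or as a net total. Surgery takes place at three hospitals, and the text does not say that they record blood loss in the same way. A used sponge carries its own dry weight, and a canister holds any fluid put in and suctioned out. Gross figures taken literally would therefore overstate blood loss. They would also add patient-to-patient scatter unrelated to bleeding.

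Blood loss is the first specific aim and the only quantity in the sample size calculation. Enough added scatter would lower power and widen the confidence interval, and inflated volumes would be hard to compare with other trials. Dry weights and instilled volumes not recorded in the operating room might not be recoverable from charts later.

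**Working it through.** **Step 1. Do the two descriptions conflict?**

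| Place | Assessor | Inputs | Formula |
|---|---|---|---|
| Study Design | operating surgeon | not stated | not stated |
| Primary outcomes, item 1 | not stated | canister volume, sponge weight | not stated |

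Each row supplies what the other leaves out, both speak of an estimate, and neither excludes the other. Read together they describe one measure. The sentence on charts is a general source statement for all variables and does not replace item 1 with an unaided guess.

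**Step 2. Reproduce the plan's sample size.** Inputs from Statistical Analysis: SD 135 mL, difference 150 mL, normal quantiles 1.96 and 1.282.

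N = 2 × 135² × (1.96 + 1.282)² / 150² = 2 × 18,225 × 10.511 / 22,500 = 17.03, which the plan gives as 17.

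The text calls alpha one-sided, but 1.96 is the two-sided 5% value. That is a separate matter. Two-sided 0.05 is used below because it matches the plan's formula and is the stricter choice.

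**Step 3. What does a common overstatement do?** If each recorded value is true loss plus an offset with mean m in both arms, the difference in means is (μ₁ + m) − (μ₂ + m) = μ₁ − μ₂. The offset drops out and only its variance remains.

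**Step 4. How much added variance can 50 per arm absorb?** Let s be the SD of the added error, assumed independent of blood loss and added to the planning SD.

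- Total SD = √(135² + s²)
- Standard error of the difference = total SD × √(2/50)
- Power from the noncentral t distribution with 98 degrees of freedom and noncentrality 150 / standard error
- 95% CI half-width = 1.984 × standard error

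Example, s = 100: total SD = √(18,225 + 10,000) = 168.0; standard error = 168.0 × 0.2 = 33.6; noncentrality = 150 / 33.6 = 4.46; power 99.3%; half-width = 1.984 × 33.6 = 66.7 mL.

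| Assumed s (mL) | Total SD (mL) | Power at 50 per arm | CI half-width (mL) | n per arm for 90% power |
|---|---|---|---|---|
| 0 | 135.0 | >99.9% | 53.6 | 19 |
| 50 | 144.0 | 99.9% | 57.1 | 21 |
| 100 | 168.0 | 99.3% | 66.7 | 28 |
| 150 | 201.8 | 95.7% | 80.1 | 40 |
| 200 | 241.3 | 86.8% | 95.8 | 56 |
| 300 | 329.0 | 61.7% | 130.6 | 103 |

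The first row needs 19 rather than 17 because the t distribution replaces the normal approximation.

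**Step 5. Break-even.** Power at 50 per arm falls to 90% when total SD = 229.1 mL, that is s = √(229.1² − 135²) ≈ 185 mL. Error would then be 185² / 229.1² ≈ 65% of all variance in the outcome.

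Every s above zero is an assumption, since the document gives no figure for instilled fluid or sponge weight. The rows at 200 and 300 mL show where the margin ends; they are not expected values.

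**The case for a change.** The strongest case for a change is that three hospitals could each comply with the text and still record different quantities. Dry sponge weight is present whether or not fluid is instilled, so that part of the overstatement does not depend on surgical practice. One sentence would settle it, and only if written before the data are collected. Power is not the only cost: at an added SD of 150 mL the interval widens from about 54 to 80 mL on each side even though power stays above 95%. The cancellation in step 3 also needs equal mean offsets. If less bleeding led to less irrigation, gross volumes would exaggerate a true difference.

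Part of this stands. The supplied text has no formula, and absolute volumes per arm would be open to question if gross values were used.

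The rest is weaker. Listing inputs for an estimate is not an instruction to add up gross values, and allowing for dry weight and instilled fluid is what a surgeon estimating blood loss would be expected to do. The unseen data collection tool may already hold those fields. Differences between hospitals act on both arms alike under randomization and blinding. If the drug has no effect, an offset linked to bleeding has the same distribution in both arms, so the test keeps its error rate. The aim is a comparison between arms, for which absolute volumes are secondary. The hematocrit-based primary outcome gives a check that uses neither canister nor sponges, although it does not define item 1.

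**Conclusion.** No change to the plan follows. The missing formula is a gap in detail that those measuring and analysing the outcome can be expected to fill sensibly: the blinded surgeon's estimate, taken from canister and sponges with the obvious deductions.

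Followed as written, the comparison between arms remains sound. A false difference between arms is not expected, and the 50 per arm chosen for side effects leaves a wide margin over the 17 calculated for blood loss. Power for 150 mL stays at or above 90% unless independent added error has an SD above about 185 mL.

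This rests on four assumptions: the planning SD of 135 mL is about right; added error is independent of true loss; blinding of the surgeon holds; and the two descriptions are read as one measure. The document does not say whether 135 mL was obtained with this kind of measurement. If it was, some of the error is already counted and the table overstates the loss of power. If the true SD is larger than 135 mL, the margin is smaller than shown.

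### Short-lived side effects of a single pre-incision dose are first asked about at 2 weeks, although finding side effects is the only stated reason for 50 rather than 17 per arm

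*Combined protocol and SAP*

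**What the plan says.** Under Study Design, tranexamic acid or saline is given as one intravenous bolus "15 minutes prior to initial surgical incision". The same section says that side effects of the medication are assessed by a "questionnaire that will be given at their post-op appointment at the 2 week and 6-week mark". The list of secondary outcomes gives diarrhea, nausea and headache as mild effects (items 8a to 8c) and shortness of breath, deep vein thrombosis and pulmonary embolism as serious ones (item 9). Both items point to Supplement 2.

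Two earlier assessments are planned: a blood draw for hemoglobin and hematocrit at 24 hours, and item 6 of the secondary outcomes, "Pain index on post-operative day 1, and 2-week post-operative visit". Neither is described as including a side-effect question. The EPIC and Allscripts charts are named as data sources, without an item, time window or abstraction rule for symptoms during the hospital stay.

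Statistical Analysis calculates 17 patients per group for blood loss and then explains the larger target: "we wish to include 50 patients on each arm to try to increase the chances of identifying any side effects associated with the procedure". No other reason is given.

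**The concern.** The drug is given once, at the start of surgery. If it causes nausea, headache or diarrhea, these may well have come and gone before the 2-week visit. A patient asked then must remember mild symptoms from the days around an operation, and some will not.

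Equal forgetting in both arms does not remove the problem. If a share s of true cases is reported, both observed rates and their difference are multiplied by s. Fewer events are seen, and a real difference is harder to detect. What is at stake is the purpose of the extra 33 patients per arm (50 − 17): they were added to find side effects, and late questioning gives back part of what they buy for short-lived symptoms. An absence of reported effects would then be weak evidence that there were none.

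**Working it through.** **Inputs from the protocol.** Questionnaire at 2 and 6 weeks (Study Design); 17 per group calculated and 50 per arm planned, with 135 ml, a 150 ml difference, 1.96 and 1.282 in the formula (Statistical Analysis); chi-square for categorical variables at P < 0.05 (Statistical Analysis).

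**Assumed inputs.** True side-effect rates and the share s of cases recalled at 2 weeks. The protocol gives neither for a single dose, so what follows is illustration, not prediction.

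**Step 1: the plan's own figure.** 2 × 135² × (1.96 + 1.282)² / 150² = 17.03, stated as 17. Power for 150 ml at two-sided 0.05 (normal approximation) is 90.0% with 17 per arm and above 99.9% with 50. The increase, 50/17 = 2.94-fold, is thus not needed for the blood-loss calculation, in line with the reason the protocol gives.

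**Step 2: chance of observing at least one case in an arm.** With true rate p, recall share s and n patients, this is 1 − (1 − p·s)^n. For p = 5%:

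| Share recalled | Observed rate | n = 50 |
|---|---|---|
| 100% | 5% | 92% |
| 75% | 3.75% | 85% |
| 50% | 2.5% | 72% |
| 25% | 1.25% | 47% |

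With full capture, 17 patients give 1 − 0.95^17 = 58%. The number of fully captured patients equivalent to 50 with recall s is 50 × ln(1 − 0.05s) / ln(0.95): about 25 at s = 50% and about 12 at s = 25%. The second figure is below 17.

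**Step 3: power to compare the arms.** Exact enumeration of the uncorrected chi-square test, 50 per arm, both rates multiplied by s:

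| Assumed true rates | s = 100% | s = 75% | s = 50% |
|---|---|---|---|
| 40% vs 20% | 60% | 44% | 30% |
| 30% vs 10% | 73% | 59% | 39% |
| 10% vs 5% | 14% | 11% | 8% |

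The last row shows that for small differences the comparison is uninformative at any recall share.

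**Step 4: does asking on day 1 help if anesthesia also causes these symptoms?** Assume an independent background rate b = 30% in both arms. The observed rate becomes 1 − (1 − p)(1 − b). For 40% vs 20% this gives 1 − 0.6 × 0.7 = 58% and 1 − 0.8 × 0.7 = 44%, and power at day 1 falls from 60% to 31%. At 2 weeks the patient is recalling the same mixed symptoms: with half recalled, the rates are 29% and 22% and power is 13%. Under these assumptions the background weakens both time points, and the early question still does better.

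**The case against.** The strongest objection is that day-1 nausea and headache partly reflect anesthesia, and that this background dilutes a difference between arms just as forgetting does. Setting 31% power at day 1 with a 30% background beside 30% at 2 weeks with half recall and no background makes the two look equal. The dilution is real and is a reason not to declare day 1 the main time point. It does not defeat an added early question, because a 2-week questionnaire asks about the same mixture (step 4).

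Second, differences of 20 percentage points are generous. Risks of Study lists side effects under prolonged use and expects few from one dose. The sample-size sentence speaks of identifying side effects, which is closer to observing cases than to powering a contrast. Both points stand, so step 2 is the more relevant illustration.

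Third, a reader might infer that these symptoms are captured by questionnaire and nothing else. The text does not support that: charts are a named source and might hold some in-hospital symptoms. But no rule says which symptoms are abstracted or over what period, and charting is not the same as asking every patient. The content of Supplement 2 is not available here, although Study Design fixes when the questionnaire is given.

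Fourth, a reader might infer that a bill for the drug would reveal the arm before the 2-week visit. The Budget section says that anesthesia bills for the drug but not when a bill reaches the patient, so this point draws nothing from it.

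**Conclusion.** The point holds for three mild secondary items, nausea, headache and diarrhea. Their first described direct assessment comes 2 weeks after a single dose, while side-effect detection is the stated reason for nearly tripling the sample. The loss could be small or large: for a 5% event, the chance of seeing a case in an arm falls from 92% to 85% at 75% recall and to 47% at 25% recall. Every event rate, recall share and background rate behind these figures is an assumption.

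A reader might go further and conclude that the trial's safety assessment as a whole, or its main result, is compromised. The documents do not support this. Both specific aims and all primary outcomes concern blood loss or blood products and do not use the questionnaire. Deep vein thrombosis and pulmonary embolism would normally be charted or reported as serious adverse events, for which Risks of Study describes a route. Because patients are blinded, poor recall should mainly lose events in both arms rather than favor one. This is an improvement to consider, not a flaw that must be corrected before the trial can answer its main question.

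**What to change.** Add the Supplement 2 questionnaire at the planned postoperative day-1 pain assessment. Keep it at 2 and 6 weeks, where it also serves later events. Report nausea, headache and diarrhea by time point and by arm, so that early and recalled symptoms can be told apart. If charts are to count as a source for these symptoms, state the items and the time window to be abstracted.

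The cost is one more short form at a contact that already exists, plus a few data fields. The drawback is that day-1 answers include symptoms due to anesthesia, which should be acknowledged when they are interpreted. There is no need to name day 1 as the main time point.

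### Primary outcome 2 multiplies blood volume by body mass index, which does not give a volume, so as written it cannot yield the blood loss in mL that aim 1 compares

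*Combined protocol and SAP*

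**What the plan says.** The first specific aim is "To compare the volume of blood loss in patients undergoing minimal invasive myomectomies who received prophylactic tranexamic acid vs placebo". Two of the three primary outcomes measure that loss:

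- Item 1 is measured directly: "Estimated blood loss at time of procedure completion; using volume of cannister and weight of lap sponges".
- Item 2 is derived: "Calculated Blood loss, using pre-operative hematocrit, postoperative hematocrit and estimated blood volume x Body Mass Index".

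The Study Design section fixes the time of the post-operative blood test: "Hemoglobin and hematocrit will be obtained 24 hours post procedure". The Statistical Analysis section plans the trial for "90 % power to detect a 150 ml difference in blood loss".

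The line in item 2 is the only definition of calculated blood loss in the protocol. There is no equation, unit, blood-volume constant or formula, or hematocrit denominator, and the Statistical Analysis section adds none. The data collection tool that the protocol mentions is not among the documents.

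**The concern.** The one operation that item 2 states, blood volume times BMI, does not produce a volume. A per-kilogram blood volume has to be multiplied by body weight to give mL, and a blood volume already in mL needs no further body-size term. BMI fits neither case.

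A treatment difference computed this way could not be read as a volume of blood. It could not be set beside item 1 or judged against the 150 mL planning difference. Nor is the error a fixed change of scale that could be undone in the report: the factor is each patient's own height or BMI, so two patients with the same true loss receive different scores.

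The damage is to the size and meaning of the estimate. Randomisation still protects the test of no difference, and the sample size does not use this formula.

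**Working it through.** **The plan's own figure.** The Statistical Analysis section uses a difference of 150 mL, an SD of 135, and normal quantiles of 1.96 and 1.282:

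2 × 135² × (1.96 + 1.282)² / 150² = 17.03, stated as 17 per group.

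The figure reproduces. It is on the mL scale and does not involve calculated blood loss as defined in item 2, so the unit problem leaves it unchanged.

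**Units.** The only input needed is BMI = weight (kg) / height² (m²). A fractional fall in hematocrit has no unit.

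| Reading of estimated blood volume | Product with BMI | Relation to the intended mL |
|---|---|---|
| Constant in mL/kg | mL/kg × kg/m² = mL/m² | divided by height² |
| Volume in mL | mL × kg/m² | multiplied by BMI |

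Neither product is in mL. This step uses no assumed patient values.

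**Effect on a true 150 mL difference.** The protocol gives no body sizes, so the heights and BMI values here are assumptions. If treatment lowers loss by 150 mL in every patient, the expected difference in scores is 150 times the average factor in the sample.

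- mL/kg reading, factor 1/height²:
  - 1.55 m: 0.416 × 150 = 62.4
  - 1.63 m: 0.376 × 150 = 56.5
  - 1.75 m: 0.327 × 150 = 49.0
- mL reading, factor BMI:
  - 22 × 150 = 3,300
  - 30 × 150 = 4,500
  - 40 × 150 = 6,000

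**One patient.** Assume 80 kg, 1.65 m, 65 mL/kg, hematocrit falling from 38 to 33, and the pre-operative value as denominator.

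- Intended: 65 × 80 = 5,200 mL; 5,200 × 5/38 = 684 mL.
- BMI: 80 / 1.65² = 29.38.
- mL/kg reading: 65 × 29.38 × 5/38 = 251.
- mL reading: 5,200 × 29.38 × 5/38 = about 20,100.

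With the mean hematocrit (35.5) as denominator, the three values are 732, 269 and 21,521. The ratios to the intended value, 0.367 and 29.38, stay the same, so the distortion does not depend on the denominator.

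**Variation between patients, mL/kg reading.** Two women of 80 kg with this same hematocrit fall have the same intended loss of 684 mL. They score 684.2 / 1.55² = 285 and 684.2 / 1.75² = 223. The ratio is (1.75/1.55)² = 1.275, a gap of about 27% from height alone. Order can also reverse: a true 600 mL loss at 1.75 m scores 600 / 1.75² = 196, while a true 500 mL loss at 1.55 m scores 500 / 1.55² = 208.

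**The case against.** The strongest reply is that item 2 lists inputs and is not an equation. It does not say how the hematocrits combine, so strictly nothing can be computed from it, and BMI is probably a slip for weight. The tool that was not supplied may hold the right formula. It is true that the patient-level scores above rest on a supplied hematocrit term and an assumed constant. The unit error does not, because it follows from the one product the line does state. If the line is only a list, then no formula for a primary outcome is fixed in advance, and the same correction is needed. If the tool holds a different formula, tool and protocol must be reconciled.

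Three further points stand in part:

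- Values in the thousands would be recognised as impossible, so the mL reading is unlikely to reach a report unnoticed. The mL/kg reading is the real risk, because 50 to 60 passes for a plausible number of mL.
- The ranges above use individual extremes of height and BMI. An arm-level difference depends on the sample's average factor, which would vary less.
- Item 1 still answers aim 1 in mL, and the protocol does not say which blood-loss measure the 150 mL refers to. A wrong derivation could also be recomputed from recorded inputs.

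These points limit the harm. They do not make the definition of item 2 correct.

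**Conclusion.** The concern holds. Followed as written, item 2 gives a quantity in mL/m² or mL × kg/m², never a volume, and its distortion differs from patient to patient. That conclusion needs only the definition of BMI. The numerical sizes are illustrations that rest on assumed heights, BMI values, hematocrits and a per-kilogram constant: a true 150 mL difference shows as roughly 49 to 62 on the more plausible reading and 3,300 to 6,000 on the other. The defect is confined to primary outcome 2. Item 1, the null test and the sample size of 17 are untouched. Because the line defines a primary outcome, it must be corrected before analysis.

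**What to change.** Replace item 2 with a complete equation in mL, fixed before analysis. For example:

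Calculated blood loss (mL) = estimated blood volume (mL) × (pre-operative Hct − 24-hour post-operative Hct) / pre-operative Hct, where estimated blood volume (mL) = [stated constant, mL/kg] × body weight (kg), or a named height-and-weight formula for women.

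The linear form and the pre-operative denominator are one option; the investigators should name their choice. What is essential is to remove the multiplication of blood volume by BMI and to state the blood-volume constant or formula, the hematocrit denominator and the unit. The data collection tool should carry the same equation, and any values already derived should be recomputed patient by patient.

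The cost is one or two sentences and no new data. Weight is already needed for the "single IV bolus injection of TXA 30mg/kg", both hematocrits are already inputs, and BMI as listed already requires height. The sample size does not change.
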